6.3 SCHEDULE OF EVENTS

Study Phase	Screening	Baseline- Intervention	Washout	Crossover- Intervention	Follow-Up	Early Termination Visit
Visit Number	1	2	3	4	5	
Visit Window		≤30 days after Visit 1	+/- 3 days 28 days after Visit 2	+/- 3 days 28 days after Visit 3	+/- 3 days 28 days after Visit 4	
Informed consent/Accent	X					
Inclusion/Exclusion criteria	X					
Historical Data/Demographics*	X					
Pancreatic Autoantibodies †	X					
Random C-peptide concentration††	X					
Randomization		X				
Pregnancy test**	X	X	X	X	X	X
Current Medical data***		X	X	X	X	X
Pubertal Tanner staging with physical exam	X					
Ht/Wt measurement and vitals	X	X	X	X	X	X
Supervised CGM insertion (and training, if applicable on use) †††		X		X		
C-peptide by 2-hr MMTT††††			X		X	X
HbA1c		X			X	X
Blood samples for biomarkers (PI:C and INS DNA)		X	X	X	X	X
Provision of HAMS-AB		X		X		
CGM download			X		X	X
Stool samples****		X	X	X	X	X
Whole blood for additional T1D testing		X	X	X	X	X
Serum and plasma for storage^		X	X	X	X	X
Adverse event assessment*****		X	X	X	X	X
Dietary Assessments*****		X	X	X	X	X
Verbal Diet recall	X					
Sampling of prebiotic	X					

Data Collection:

***Historical data:** Date of birth, sex, Race/Ethnicity, date of diagnosis of T1D.

**To be done in girls of reproductive potential.

*****Current Medical Data (All visits except screening):** Medication use including types of insulin, means of insulin administration, and total daily insulin dose (u/kg body weight, averaged over the 3 days prior to each study visit), use of other medications.

******Stool samples** will be collected at home using a kit (Zymo feces catcher and RNA/DNA shield fecal collection tubes) within 3 days of presentation to each visit.

*****Participants will be assessed for **safety** with questions regarding general well-being as well as specific questions to evaluate for adverse events. Participants will also be questioned about stool form and frequency, gastrointestinal symptoms, fevers, or infection.

*******Dietary Assessments** will be ideally obtained using the Automated Self-Administered 24-Hour (ASA24) dietary assessment tool [46-48], a web-based tool for administering automatically coded, self-administered recalls/food records. This will allow assessment of dietary fiber intake along with other dietary components. Participants will be asked to fill these in for the 24 hrs. diet recall prior to each stool collection in a time frame of +/- 3 days from the stool sample collection. This can also be completed during the study visit. Diet diaries will be accepted in lieu of the online questionnaire. Participants will be asked to record all meals and snacks, time of day, number of servings, major food components or description (for example chicken or protein), estimated portion sizes and whether they completed the meal or not, and any drinks including water.

†Pancreatic autoantibodies to be tested only in those with no evidence of being tested for antibodies in their medical chart to confirm T1D.

††Random, non-fasting c-peptide: C-peptide level will be analyzed at Indiana University Translation Core Lab using a two site immuno-enzymometric assay using a Tosoh 2000 auto-analyzer (TOSOH, Biosciences, Inc., South San Francisco, CA). The C-peptide assay is calibrated against the WHO IS 84/510 standard and has a sensitivity level of 0.05 ng/mL.

†††At visit 2 (baseline/intervention) and 4 (crossover), a blinded CGM sensor will be inserted in those participants who are not currently using a CGM as part of their routine care. Training will be provided on calibration of the sensor, its use in blinded mode, and sensor insertion. Participants will be reminded to insert a sensor at home after approximately 14 days and continue using the blinded sensor for an additional 14 days. Participants will use their own home blood glucose meter or (if had been previously using one) CGM for regular blood glucose monitoring. The participant will return after 4 weeks to assess the CGM data. CGM must be used for at least 200 hours (equivalent to 8.3 days out of 14 days)

††††C-peptide by 2-h MMTT: 2-hour MMTT will be performed using the standardized protocol utilized by the TrialNet Centers [51]. The early discontinuation MMTT will only be done if it has been at least 6 weeks since the last MMTT.

^Serum and Plasma for storage – subject has option to consent or deny storage. Will be used for future type 1 diabetes research assays.

6.4 STUDY VISITS

Visit 1 – Screening

This visit will be at the hospital or research center. It will last approximately 1-2 hours and will include:

- Obtain informed consent/assent documents and determine inclusion and exclusion criteria
- Measurement of height and weight to determine BMI percentile eligibility and physical exam including pubertal staging
- Obtaining Vital signs (heart rate, temperature, blood pressure, and respiratory rate)
- Obtaining medical history
- Dietary assessment by verbal recall
- Obtaining blood sample (approximately 1.5 tablespoon) – Random non-fasting c-peptide, pancreatic autoantibodies if not previously done to confirm T1D diagnosis
- For female adolescents: urine will be collected for a pregnancytest
- Subject to sample prebiotic for palatability to ensure compliance

Visit 2 – Baseline-Intervention

This visit will be at the hospital or research center. It will last approximately 1-2 hours and will include:

- Measurement of weight and bedside nurse assessment such as general appearance, respiratory and cardiac assessment.
- Obtain vital signs (heart rate, temperature, blood pressure, and respiratory rate)
- Collecting a diet history (diary or questionnaire)
- Collecting Adverse Events (if applicable)
- Obtaining medical history and insulin use

Obtaining blood samples (approximately 2 tablespoons) – HbA1c, Serum biomarkers of beta cell stress and death (PI:C and INS DNA), other T1D testing, and serum and plasma for storage.

- Some of the blood will be stored for future T1D research use

- CGM placement and training for participants not currently using one.
- For female adolescents: urine will be collected for a pregnancytest
- Collecting stool samples prior to or the morning of the visit (a stool collection kit will be shipped to the participants once eligibility is confirmed)
- Study Randomization to either supplement or standard of care diabetes management and a diabetic diet.
– Supplement (HAMS-AB) will be provided and will be taken by mouth twice daily with food such as apple sauce or oatmeal as described in Section 6.2. Instructions will be provided for recommendations on a healthy diabetic diet.
- A new stool collection kit will be provided for the next visit

Visit 3 - Washout

This visit will be at the hospital or research center. It will last approximately 2-4 hours and will include:

- Measurement of weight, assessment of CGM insertion sites, as well as bedside nurse assessment such as general appearance, respiratory and cardiac assessment.
- Obtaining Vital signs (heart rate, temperature, blood pressure, and respiratory rate)
- Collecting a diet history (diary or questionnaire)
- Collecting Adverse Events (if applicable)
- Obtaining medical history and insulin use
- CGM download
- For female adolescents: urine will be collected for a pregnancytest
- Collecting stool samples prior to or the morning of the visit
- Obtaining fasting blood sample (approximately 5 tablespoons) – Serum biomarkers of beta cell stress and death (PI:C and INS DNA), other T1D testing, and serum and plasma for storage and MMTT

- samples (see below), and serum and plasma for storage
 - Some of the blood will be stored for future T1D research use
- Completion of a mixed meal tolerance test (MMTT). See below.
- After completion of this visit, participants will be instructed to follow a regular diet with no supplement intake for the following 4 weeks and to follow standard diabetes care as instructed by their diabetes provider.
- A new stool collection kit will be provided for the next visit

Preparing for an MMTT

- Subjects will be asked to fast except for water for at least 10 hours prior to visit.
- Subjects will be asked to limit strenuous activity for at least 10 hours prior to visit.
- Subjects will be asked to consume at least 150 g of carbohydrates each day for 3 days.
- If subject experiences hypoglycemia, morning of the visit, subjects will be instructed to treat low blood sugar and to reschedule MMTT procedure.

MMTT Visit procedures

Blood glucose will be tested and the MMTT started if blood glucose <200 by 10:00am. Long-acting insulin may be taken per routine, but short acting insulin must not have been given within 2 hours of MMTT.

An IV catheter will be placed in the arm by trained nurses for blood drawing purposes. Blood will be drawn 10 minutes prior to drinking Boost, just prior to drinking Boost, 15, 30-, 60-, 90-, and 120-minute post Boost consumption. High Protein Boost will be measured to a dose of 6ml/kg body weight (maximum dose 360ml). Total volume of blood will be approximately (5 tablespoons) not to exceed 5ml/kg/day.

Visit 4 Crossover-Intervention

This visit will be at the hospital or research center. It will last approximately 1-2 hours and will include:

- Measurement of weight, assessment of CGM insertion sites, as well as bedside nurse assessment such as general appearance, respiratory and cardiac assessment.
- Obtaining vital signs (heart rate, temperature, blood pressure, and respiratory rate)
- Collecting a diet history (diary or questionnaire)
- Collecting Adverse Events (if applicable)
- Obtaining medical history and insulin use
- Obtaining blood samples (approximately 2tablespoon) – Serum biomarkers of beta cell stress and death (PI:C and INS DNA), other T1D testing, and serum and plasma for storage
 - Some of the blood will be stored for future T1D research use
- For female adolescents: urine will be collected for a pregnancytest
- Supplement (HAMS-AB) will be provided and will be taken by mouth twice daily in the treatment arm as above in addition to insulin for diabetes management. Those in the control arm will follow standard diabetes management in addition to a recommended diabetic diet.
- New CGM supplies given, if applicable.
- Collecting stool samples 3 days prior to or the morning of the visit
- A new stool collection kit will be provided for the next visit

Visit 5 Follow-Up and/or Early Termination Visit

This visit will be at the hospital or research center, will last approximately 2-4 hours and will include:

- Measurement of height and weight and assessment of CGM insertion sites
- Obtaining vital signs (heart rate, temperature, blood pressure, and respiratory rate)
- Collecting a diet history (diary or questionnaire)
- Collecting Adverse Events (if applicable)

- Obtaining medical history and insulin use
- Obtaining blood samples (approximately 5 tablespoons) – HbA1c, Serum biomarkers of beta cell stress and death (PI:C and INS DNA), MMTT samples (see above), other T1D testing, and serum and plasma for storage
 - Some of the blood will be stored for future use
- For female adolescents: urine will be collected for a pregnancy test
- Completion of a mixed meal tolerance test(MMTT) See Visit 3 for details.
- CGM download
- Collecting stool samples prior to or the morning of the visit

An early discontinuation MMTT will only be done if it has been at least 6 weeks since the last MMTT.

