AIM 1: Determine the effect of HAMS-AB on the gut microbiome profile and SCFA production in children with recently diagnosed T1D. We *hypothesize* that HAMS-AB consumption will shift the gut microbiome to microbial populations that are capable of HAMS-AB fermentation and increase SCFA production. Twelve youths (11-17 years old) will consume HAMS-AB or follow the standard of care recommended diabetic diet daily for [49,50] 4 weeks and then cross over after a 4-week washout period. DNA will be extracted from fecal samples obtained followed by 16S RNA sequencing for gut microbial community analysis at baseline and at each visit during the study period [32, 33]. SCFAs will be analyzed using standard methods [36, 37].

AIM 2: Determine the effect of HAMS-AB on glycemia and β -cell function and health. We *hypothesize* that the prebiotic HAMS-AB will improve overall glycemia including reducing glycemic variability in recently diagnosed persons with T1D. We will compare glycemic/ β -cell measures pre/post intervention with HAMS-AB and between the intervention and control groups. We will measure glycemia using HbA1c, average glucose and glucose variability using continuous glucose monitoring (CGM) [38-40]. We expect to see an improvement in glycemia in response to HAMS-AB intake. We will assess β -cell function using mixed meal tolerance (MMTT)-derived C-peptide measures. We *expect* that measures of β -cell stress/death will show improvement following the use of HAMS-AB. We will determine β -cell stress using proinsulin/C-peptide (PI:C) ratios [41]. We will assess β -cell death by differential methylation of proinsulin (INS) DNA [42].

Upon successful completion of this pilot study, we expect to assess the effect of prebiotic administration on the gut microbiome profile, SCFA production, glycemia and β -cell function in humans with T1D. The knowledge generated by the proposed research will provide critical experimental information needed to substantiate a fully powered study.

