33 ENROLLMENT

Up to 24 subjects will be screened to find 12 adequate subjects eligible for enrollment.

The plan is to recruit 24 patients with the goal of having 50% eligible and enrolled. Once 12 participants have completed the 12 week visit, we will stop recruitment. At Indiana University, as per our current recruitment strategies for other new-onset studies, patients with newly diagnosed T1D will be approached whenever possible when inpatient at diagnosis and then re-contacted after discharged home. Visits will be conducted at the Indiana Clinical Research Center (ICRC) and coordinated with diabetes clinic follow-up visits when possible.

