34 STUDY ENDPOINTS

The primary outcome assessment will be to assess changes in the gut microbiome profile in response to HAMS-AB. Secondary outcome measures will be changes in SCFA production, changes in glycemia, pro-insulin to C-peptide ratios as a marker of β cell ER stress. Other β cell stress markers including unmethylated insulin DNA will also be measured. We will also examine glycemic outcomes and β cell function as assessed by responses to MMTT, although given the variability in these measures in other reported studies of new-onset T1D [43] we do not expect to be adequately powered in this small trial to see significant differences in these outcomes.

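### PI:C is sampled under fasting MMTT preparation at the period ends but under unstated conditions at the period starts, so the within-HAMS-AB pre/post change in Aim 2 cannot be separated from sampling conditions

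*Combined protocol and SAP*

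**What the plan says.** Aim 2 (Section 1.2) plans to compare glycemic and beta-cell measures "pre/post intervention with HAMS-AB and between the intervention and control groups", and takes PI:C as its marker of beta-cell stress. The study endpoints section (printed as 34) lists "pro-insulin to C-peptide ratios as a marker of" beta-cell ER stress among the secondary outcomes. Section 3.1 adds an assessment of durability after washout in those who received the prebiotic.

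The Section 6.3 schedule places the PI:C draw at Visits 2, 3, 4 and 5 and at early termination. The Section 6.4 visit descriptions differ:

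- Visit 2, start of period 1: "Obtaining blood samples (approximately 2 tablespoons) – HbA1c, Serum biomarkers of beta cell stress and death (PI:C and INS DNA". No MMTT and no fasting instruction.
- Visit 3, end of period 1: "Obtaining fasting blood sample (approximately 5 tablespoons) – Serum biomarkers of beta cell stress and death (PI:C and INS DNA". The MMTT preparation includes "Subjects will be asked to fast except for water for at least 10 hours prior to visit".
- Visit 4, start of period 2: "Obtaining blood samples (approximately 2tablespoon) – Serum biomarkers of beta cell stress and death (PI:C and INS DNA". No MMTT and no fasting instruction.
- Visit 5, end of period 2: the draw line does not mention fasting, but the visit includes an MMTT and refers back to Visit 3 for its details.

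Section 8.0 specifies t-tests for continuous variables and no adjustment for sampling conditions.

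**The concern.** PI:C has C-peptide as its denominator. The protocol itself measures beta-cell function by the C-peptide response to a mixed meal, so it relies on C-peptide moving with food. Unless proinsulin moves in the same proportion, the ratio depends on when the participant last ate.

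The difference in preparation follows the pre/post axis exactly: both period ends carry the MMTT conditions and both period starts carry none. A change from Visit 2 to Visit 3, or from Visit 4 to Visit 5, could therefore reflect HAMS-AB, a change in sampling conditions, or both. For participants given HAMS-AB first, the durability comparison from Visit 3 to Visit 4 has the same problem in reverse.

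The pilot's stated purpose is to estimate effect sizes for a later trial, so a change score that carries a sampling artefact would pass into that trial's planning.

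**Working it through.** The plan gives no figure to reproduce: 12 participants is a rule of thumb, and no SD, effect size or meal effect for PI:C is stated. The check is first a comparison of texts, then an illustration under labelled assumptions.

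**Step 1. Sampling conditions by visit (Sections 6.3 and 6.4).**

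| Visit | Place in design | MMTT | Condition of the PI:C draw |
|---|---|---|---|
| 2 | start, period 1 | no | not stated |
| 3 | end, period 1 | yes | fasting, stated |
| 4 | start, period 2 | no | not stated |
| 5 | end, period 2 | yes | fasting, by reference to Visit 3 |
| Early termination | varies | only if at least 6 weeks since the last | not stated if no MMTT |

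The MMTT visits also carry a 10:00am condition on starting the test, a 3-day carbohydrate instruction and a 2-hour restriction on short-acting insulin. None of these is stated for Visits 2 and 4. The schedule footnotes add nothing. Elsewhere the protocol does name the meal state when it wants one: the screening C-peptide is described as random and non-fasting.

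On early termination: Visit 3 falls at day 28, so 6 weeks later is day 28 + 42 = 70. Visit 4 is at day 56. A participant who leaves during washout or in the first 2 weeks of period 2 would have PI:C drawn without an MMTT, so no fast would be required.

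**Step 2. Which comparisons are exposed.** Let m be the mean shift in PI:C (end minus start) due to sampling conditions alone, and let T and C be the true changes on HAMS-AB and control.

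- Within-HAMS-AB change: T + m. The shift stays.
- HAMS-AB change minus control change: (T + m) − (C + m) = T − C. A constant shift cancels.
- End-of-period contrast, Visit 3 versus Visit 5: both under MMTT preparation, so m does not enter.
- Noise: if meal state adds independent variance v to each period-start value, the difference of changes carries an extra 2v. The end-of-period contrast carries none of it.

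**Step 3. Sign and size on the ratio scale (assumed inputs).** Suppose eating multiplies C-peptide by f and proinsulin by g. A fed start and a fasting end give a spurious change of f/g − 1.

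- f = 2.0, g = 1.5: 2.0/1.5 − 1 = +33%
- f = 1.5, g = 2.0: 1.5/2.0 − 1 = −25%
- f = 2.5, g = 1.5: 2.5/1.5 − 1 = +67%
- f = 1.5, g = 2.5: 1.5/2.5 − 1 = −40%
- f = g: 0

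If only half the period-start samples were fed, the geometric-mean change is (f/g)^0.5 − 1: √1.333 − 1 = +15% in the first case and √0.75 − 1 = −13% in the second. If all were fasting, it is 0.

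**Step 4. Effect on the pre/post test (assumed shift).** Two-sided 5% paired t-test, n = 12, 11 degrees of freedom, critical value 2.201, no treatment effect. With the shift s in SD units of the within-person change, the noncentrality is s√12.

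| s | s√12 | False-positive rate |
|---|---|---|
| 0 | 0 | 5% |
| 0.25 | 0.87 | 12% |
| 0.5 | 1.73 | 35% |
| 0.75 | 2.60 | 66% |
| 1.0 | 3.46 | 88% |

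A simulation of 40,000 null trials agreed with the pre/post rates at 0, 0.5 and 1.0 (5.1%, 35.4%, 88.4%). At the same shifts, HAMS-AB change minus control change was rejected in 4.8%, 4.9% and 4.9% of trials, with mean bias about 0.

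**The case against.** The strongest reply is that the protocol is silent about Visits 2 and 4, and silence does not mean fed. The statement that visits are "coordinated with diabetes clinic follow-up visits when possible" covers all visits, so it does not separate starts from ends. The randomized comparison, which Aim 2 also plans, is largely protected. What remains is an uncontrolled within-arm change in a secondary marker of a 12-person pilot, and Section 8.0 spells out a pre/post calculation only for the microbiome diversity index.

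Most of this stands, and it rules out several stronger readings that a reader might infer:

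- *That the start samples are fed and all end samples fasting.* No passage says how Visits 2 and 4 are run. Visit 5 is fasting only by cross-reference, and the protocol does not say which of that visit's seven MMTT sampling times supplies the PI:C tube. Early-termination samples may have no fast at all.
- *That the bias works against the hypothesis, or has a known size.* That needs f > g and fed baselines, and the documents support neither. Step 3 gives either sign.
- *That the treatment comparison is invalid.* A constant shift cancels. Bias would need meal state at Visits 2 and 4 to differ by sequence or visit.
- *That INS DNA is equally affected.* The argument rests on C-peptide as the denominator and does not carry over.

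The reply does not rescue the pre/post PI:C comparison. Aim 2 promises it, and with no condition stated at the starts, nothing in the data would show whether sampling conditions were the same. Diet records ask for meal times, but they are tied to stool collection within 3 days, not to the blood draw.

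**Conclusion.** The point holds for the within-HAMS-AB pre/post change in PI:C and for the Visit 3 to Visit 4 durability comparison: a plan followed as written leaves each inseparable from a possible systematic difference in sampling conditions. The shift would be zero only if meals move proinsulin and C-peptide in proportion, or if the Visit 2 and Visit 4 samples happen to be fasting. Its sign and size cannot be derived from the documents. The −40% to +67% span and the 12% to 88% error rates are illustrations that depend entirely on the assumed f, g and s.

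The HAMS-AB minus control contrast keeps its validity under a constant shift and loses only precision if the uncontrolled start values are used. The primary microbiome outcome is not touched. This should be corrected, because a nearly free remedy exists in samples already planned.

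**What to change.** 1. In Section 8.0, state that the PI:C treatment comparison is the within-participant end-of-period contrast, Visit 3 versus Visit 5.
2. In Section 6.4, state that the PI:C tube at both visits is the pre-Boost sample.
3. State that early-termination PI:C samples taken without an MMTT are excluded from this contrast or flagged.
4. Label pre/post PI:C change, including Visit 3 to Visit 4, as descriptive. Record time since last meal and last short-acting insulin at every PI:C draw.

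This costs protocol wording and two short items on the case report form, with no added visit, blood draw or assay. The downside is that the contrast does not use the period-start values, and the pre/post PI:C claim is given up.

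If the sponsor wants to keep that claim, the sampling conditions at Visits 2 and 4 must match those at Visits 3 and 5. The sponsor would have to weigh the burden on insulin-treated adolescents: the protocol already provides for morning hypoglycemia and rescheduling around the MMTT.
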